PROTOCOL TITLE: Wearable device intervention to improve sun behaviors in melanoma survivors

VERSION DATE: 07/19/2021

as Co-Investigator on an industry-funded pilot project using Internet-enabled scales as weight monitoring and feedback devices to foster behavior change to support healthy weight loss ("Weigh By Day Pilot Study," PI: [name]). The experience gained from these studies in overcoming challenges associated with the distribution to, and training of participants in the use of electronic monitoring devices, as well as data collected, data summarization and reporting will ensure the successful use of monitoring devices in the proposed study.

2.3. Existing Literature:

Previously, no interventions to promote healthy sun protection behaviors have been studied in melanoma survivors. Prior studies have typically focused on individuals at moderate to high risk of developing skin cancer but not melanoma survivors ¹⁹⁻²¹. One model for behavior change that has been effective in other areas of preventive health is the Fogg Behavior Model ²². According to this model, the drivers of behavior are: 1) motivation, 2) ability, and 3) triggers. Technology can be a useful tool to implement these drivers. New wearable technologies, which fall under the umbrella of ecological momentary interventions, incorporate UVR sensors to track exposure in addition to tracking other behaviors such as physical activity. This technology may be an important addition to melanoma prevention because prior exercise and activity interventions have not addressed sun exposure and protection and a recent analysis of national U.S. data suggest that higher physical activity is associated with sunburn ²³.

3. Study Endpoints/Events/Outcomes

3.1. Primary Outcome:

Sun protection habits index, measured using Glanz et al., 2008 questionnaire, will be scored by taking the average of 6 protective behaviors (wearing a shirt with sleeves, wearing sunglasses, staying in the shade, using sunscreen, limiting time in the sun, and wearing a hat) on a 4-point ordinal scale ranging from 1 = rarely or never to 4 = always. This has been used previously in similar intervention studies ¹⁹

3.2. Secondary Outcomes:

- Sunburn during the intervention period
- Each sun protection behavior separately
- Sun/UVR exposure (The device will provide objective measures of daily UVR exposure)

- Sun protection knowledge

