Study Procedures. Users will be asked to wear the devices and sync it with the mobile app every day for 12 weeks, regardless of planned physical or outdoor activities. The study coordinator will view the data of all participants (both intervention and control) weekly to monitor device use. The study coordinator will contact participants who do not use their device more than 3 days in any given week to determine barriers and encourage use. Participants will be asked to complete periodic surveys and return the device via mail at the end of the intervention period.

Data Collection. Study measures will be collected via online surveys (in REDCap ³³) and the Shade device. The survey will be accessible anywhere with an internet connection, see section 6.0. Self-administered questionnaire data will be collected at the start of the intervention (week 0), week 4, week 8 and week 12 (end of intervention), and week 64 (1 year after the end of the intervention; the end of the following summer). After completing the surveys, participants will be directed to the study website. Survey measures and their purpose are detailed in Table 2.

Table 2. Study Measures.				Weeks				
Measure	Purpose	Description	# Items	0	4	8	12	64
Health behaviors	Distraction	Measures of healthy behaviors, including alcohol, smoking, fruits, vegetables, vitamin D, height, weight	10	X	X	X	X	X
Physical activity	Secondary outcome (unintended consequence)	Strenuous, moderate and mild activity times per week and amount of time per session	6	X	X	X	X	X
Sun Protection Habits	Primary outcome	Use of sunscreen, hat, shirt and shade while in the sun; Likert scale	14	X*	X*	X*	X*	X*
Sunburns	Secondary outcome (efficacy)	How many times did you have a red OR painful sunburn that lasted a day or more?	1	X**	X*	X*	X*,**	X**
Sun Exposure and other Protection measures	Validation/Comparison with device data	Exposure during weekday and weekend days, sunscreen details, indoor tanning	11	X**	X*	X*	X*	X**

PROTOCOL TITLE: Wearable device intervention to improve sun behaviors in melanoma survivors

VERSION DATE: 07/19/2021

Beliefs, Intentions, Self-Efficacy regarding sun protection behaviors	Substudy (if intervention fails)	Reasoned Action Battery: Intention, Attitude, Behavioral beliefs, Normative pressure, Normative beliefs, Self-efficacy	84	X			X (60)	X (60)
Sun protection knowledge	Secondary outcome (efficacy)	Knowledge of sun protection (items covered in brochure)	6	X			X	X

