Hospital Anxiety and Depression Scale	Secondary outcome (unintended consequence)	Screen for depression and anxiety used frequently in cancer survivors; Likert scale	14	X			X	X
Comorbidities	Background		14	X			X	X
Diagnosis and treatment	Background/ Potential moderators	Year diagnosis, location, stage, treatments received, recurrence, metastasis	18	X				
Fear of recurrence	Background/ Potential moderator	Cancer and health worry	5	X			X	X
Demographics	Background/ Potential moderators	Sex, age, race/ethnicity, education, income, marital status, parent status, family history of cancer, skin phenotype	15	X				
Device use			9		X	X	X	
Device satisfaction			17				X	
Total number of items				198	51	51	167	141

* Time frame: past 4 weeks

** Time frame: past summer

5.3. Study Duration:

While the entire study will take approximately 4 years in total, each participant will only be enrolled for a little longer than 1 year (12-week intervention implementation period, and follow up survey at 64-weeks).

5.4. Individually Identifiable Health Information:

HealthPartners will obtain patient name, address, email address, and telephone number based on melanoma diagnosis to contact potentially eligible participants. Among those who agree to participate in the study, we will obtain signed Health Insurance Portability and Accountability Act (HIPAA) authorization forms to seek data from HealthPartners and store

PROTOCOL TITLE: Wearable device intervention to improve sun behaviors in melanoma survivors

VERSION DATE: 07/19/2021

information regarding their melanoma diagnosis, including date of diagnosis and disease stage. These data will supplement the self-reported data.

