Participants will be provided gift cards by mail throughout the study period as they complete study procedures. They will receive \$20 following completion of the baseline survey, \$10 for the week 4 survey, \$10 for the week 8 survey, \$60 for returning the device at the end of the study period and completing the week 12 survey, and \$20 for the week 64 survey (for a total of up to \$120). In addition, a lottery-based incentive will be used to promote adherence. This incentive structure will indirectly support behavior change by incentivizing use of the devices rather than directly incentivizing the direct sun-exposure behavior. Participants will be entered into weekly lotteries for \$100 gift cards for the duration of the intervention period (12 weeks; lotteries will be held up to 16 weeks given the rolling recruitment). The weekly winners will be randomly drawn from all participants. The randomly selected winners will only be eligible for the prize if they wore the device at least 5 days during that week, as evidenced by activity data. We will email the study group every week indicating that

PROTOCOL TITLE: Wearable device intervention to improve sun behaviors in

melanoma survivors

VERSION DATE: 07/19/2021

the lottery was drawn, a winner was chosen, and the number of draws required to obtain a participant who was eligible to win.

12. Withdrawal of Participants

12.1. Withdrawal Circumstances:

No participant will be withdrawn from the study against their will.

Participants will only be withdrawn from the study if they ask to withdraw or become too ill or die prior to completing the study. If participants become too ill, they will not be withdrawn from the study until they have given their voluntary consent for study withdrawal.

12.2. Withdrawal Procedures:

Participants that withdraw from the study for any reason will be noted in the REDCap study database and will no longer receive contact from study personnel. The data collected up until that point will be used in data analysis unless otherwise requested by the participant.

12.3. Termination Procedures:

Participants will not be terminated from this study without their consent as this is a randomized controlled trial and all participants are to be followed regardless of their device use.

13. Risks to Participants

13.1. Foreseeable Risks:

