13.2. Reproduction Risks: N/A

13.3. Risks to Others: N/A

14. Potential Benefits to Participants

14.1. Potential Benefits:

There are likely no direct benefits to individual participants. Individuals in both groups may increase their activity level during the study period due to prompting from the device. Should the intervention be effective, participants may increase their awareness about melanoma and risk factors for a second melanoma and may decrease their own risk through improved UVR exposure protection habits.

15. Statistical Considerations

15.1. Data Analysis Plan:

All questionnaires have been previously developed and implemented and will be scored using standard methods.

15.2. Power Analysis:

Anticipating 85% of those recruited to the study complete the 12 week follow-up survey, a sample size of N=314 participants with outcome data is expected. A sample size of 314 will achieve 95% power to detect an effect size of 0.40 between intervention and control groups using a two-sided two-sample t-test assuming a significance level of 0.05. The effect size is similar to that found in an intervention to promote sun protection behaviors in high-risk individuals with the same primary outcome ¹⁹. Importantly, it will also achieve 70% power to compare report of sunburn during the intervention period between the two groups (detect 20% of the control participants reporting a sunburn – as seen in our preliminary data - and 10% of the intervention participants reporting a sunburn) as statistically significant at 0.05 significance level.

15.3. Statistical Analysis:

PROTOCOL TITLE: Wearable device intervention to improve sun behaviors in melanoma survivors

VERSION DATE: 07/19/2021

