Secondary analyses will focus on each self-reported sun protection behavior separately, sunburns, intentional tanning, skin cancer knowledge, and physical activity and health behaviors by comparing the intervention and control participants over the study intervention period and 1 year post-completion. Analyses will be conducted using Chi-squared and t-tests as appropriate for univariate analyses at each time point and logistic and linear regression models for multivariate analyses. Daily UVR data (minutes of UVR exposure per day) will be summarized using the area under the curve (AUC) over the 12 week intervention period. Proper transformation (e.g. log-transformation) will be applied if the AUC data are skewed. The two groups' AUC will be compared using similar methods as proposed above. The association between sun exposure and its potential moderating effect on sun protection behaviors during the intervention will be investigated using linear mixed effects models including main and interaction effects, adjusting for potential confounders. To address any potential intervention effects in the control group, we will compare the baseline and post-intervention sun protection behaviors scores using paired t-tests, stratifying by randomization group. The proportions of survivors in the intervention and control groups with potentially clinically significant depression and anxiety will be compared using Chi-squared tests and supplemented with multivariate logistic regression models. Finally, descriptive statistics will be used to summarize the implementation metrics

PROTOCOL TITLE: Wearable device intervention to improve sun behaviors in

melanoma survivors

VERSION DATE: 07/19/2021

both across and within randomization group both between Waves 1 and 2 and after completion of the study.

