Appendix: Summary of Protocol Changes and Rationale – 01/27/2020

Major changes:

1. The original version of this protocol was funded by the American Cancer Society. We also received funding for usability and a pilot study version of this proposed work from the Melanoma Research Alliance (protocol STUDY00002107/2018NTLS002). We negotiated to combine the funding to support one larger study to increase our power for experience of sunburn during the intervention period, a key secondary outcome. Therefore, we have increased the sample size here from 248 to 368 (184 each wave/summer) and we will formally close the previous pilot study with the CPRC, IRB and CT.gov and add the Melanoma Research Alliance as a funding source for this protocol. The PI discussed this plan of action with [name] on 1/24/2020 who agreed this would likely be the best path from the IRB perspective.
2. After our usability testing we have decided to switch to a different wearable device than originally proposed. This device, Shade, was developed in collaboration with the NIH NCI and has been shown to be significantly more accurate than our previously proposed device. One disadvantage of this device is that it does not objectively measure physical activity as the previous device did and therefore those pieces were removed from the protocol. We will rely on self-report measures of physical activity to test our secondary hypotheses related to physical activity. Additionally, this device is significantly more expensive than the previously planned device and therefore participants will be asked to return the device at the end of the intervention period and be provided gift cards throughout the study as incentive instead. They will be provided up to \$120 in gift cards if they complete all study procedures (\$20 baseline survey, \$10 week 4 survey, \$10 week 8 survey, \$60 return device and complete week 12 survey, \$20 complete week 64 survey).
3. As this is a minimal risk study, we have removed the during-study monitoring of anxiety and depression. We have found in another study of cancer survivors that this monitoring and sending of letters often confuses and distresses participants. We will plan, however, to examine whether rates of anxiety and/or depression rise during the intervention period (week 12 vs. baseline) following Wave 1. While we do not expect that to be the case, should it happen we will proactively monitor in Wave 2.

Minor changes:

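### Sunburn during the intervention is powered as one 12-week proportion, but section 15.3 names only per-time-point tests and gives no rule for building that proportion from the survey items

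*Combined protocol and SAP*

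**What the plan says.** Section 3.2 lists the outcome as "Sunburn during the intervention period". Section 15.2 claims "70% power to compare report of sunburn during the intervention period between the two groups", at 20% in controls and 10% in the intervention arm. The Appendix (major change 1) explains that funding was combined and the sample enlarged from 248 to 368 "to increase our power for experience of sunburn during the intervention period, a key secondary outcome".

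The instrument is one count item in Table 2 (section 5.2): "How many times did you have a red OR painful sunburn that lasted a day or more". Weeks 4 and 8 ask about the past 4 weeks. Week 12 carries two marks, one for the past 4 weeks and one with the footnote "Time frame: past summer". Weeks 0 and 64 carry the past-summer mark only.

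Section 15.3 names sunburn among outcomes to be compared between arms across the intervention period and one year afterwards. The method follows: "Analyses will be conducted using Chi-squared and t-tests as appropriate for univariate analyses at each time point", plus logistic and linear models for multivariate analyses.

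On timing, section 5.2 has devices mailed in early summer after randomization, and section 11.4 notes that "lotteries will be held up to 16 weeks given the rolling recruitment" for a 12-week intervention.

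**The concern.** The powered quantity is a single yes/no per participant over 12 weeks. The only univariate test rule works time point by time point, and no time point has an item whose window is those 12 weeks. Nothing says how the counts become one yes/no, whether the count or the proportion is tested, which week 12 recall applies, or how a missed week 4 or 8 survey is handled for this endpoint. The gap stands out because section 15.3 fixes the time point and test for the primary outcome and gives a 12-week summary (AUC) for the UVR data.

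Taken literally, the rule gives separate 4-week comparisons or a past-summer comparison. A 4-week window holds fewer events. The past-summer item may count burns that occurred before the device could have any effect. Several analyses with quite different power are open, and the choice could be made after the data are seen. This is the endpoint cited as the reason for enlarging the trial.

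**Working it through.** **Inputs.** From section 15.2: 314 participants with outcome data, 20% vs 10%, significance level 0.05, stated power 70%. From section 5.2: 1:1 allocation, so n = 157 per arm. (368 × 0.85 = 312.8, close enough to 314.) Sidedness is not stated for sunburn and is taken as two-sided, as for the primary test.

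**Formula.** With d = p1 − p2 and p̄ the mean of p1 and p2:

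power = Φ{ [d − 1.96·√(2p̄(1−p̄)/n)] / √([p1(1−p1)+p2(1−p2)]/n) }

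**1. The plan's figure.** p̄ = 0.15. √(2 × 0.1275/157) = 0.0403, times 1.96 = 0.0790. √(0.25/157) = 0.0399. (0.100 − 0.0790)/0.0399 = 0.53, and Φ = **70.1%**. The stated 70% reproduces for one 12-week proportion.

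**2. One 4-week window.** The documents do not say how burns spread over the 12 weeks, so three assumptions are shown.

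| Assumption | Control | Intervention | Power |
|---|---|---|---|
| Window captures one third of those who burn | 6.7% | 3.3% | 27.2% |
| Constant independent risk: 1 − 0.8^(1/3), 1 − 0.9^(1/3) | 7.2% | 3.5% | 31.1% |
| Window captures half of those who burn | 10% | 5% | 39.0% |

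One third is the floor for the average window, reached when nobody burns in more than one. A window would have to capture three quarters of all who burn (15% vs 7.5%) for power to reach 55.7%.

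Three separate tests at 0.05 would also carry a familywise error of up to 1 − 0.95³ = 14.3% if independent.

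**3. The week 12 past-summer item.** Let w be the summer weeks before the device, with both arms at the control rate in those weeks. Then p1 = 1 − 0.8 × 0.8^(w/12) and p2 = 1 − 0.9 × 0.8^(w/12). The value of w is assumed.

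| w (assumed) | Control | Intervention | Power |
|---|---|---|---|
| 1 | 21.5% | 11.7% | 64.9% |
| 2 | 22.9% | 13.3% | 60.2% |
| 4 | 25.7% | 16.5% | 52.3% |
| 6 | 28.4% | 19.5% | 45.8% |

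If the 20% is instead taken to cover the whole recalled summer, with the device-period effect unchanged, the same four values of w give 61.7%, 54.3%, 42.5% and 34.1%.

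**4. All three 4-week items combined.** The windows at weeks 4, 8 and 12 together span the 12 weeks. At least one burn on any of them is the quantity in step 1, so power stays at 70.1% on the plan's inputs, before any loss from missed surveys.

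**The case against.** A reader might infer that the plan tests a different endpoint from the one it powers. The documents do not show that. The sentence just before the quoted test rule says arms are compared across the intervention period, which agrees with 3.2 and 15.2. The test rule is generic text for several outcomes and is qualified as applying where appropriate. A reader might also infer that every way of following the plan loses power. That is not so either: combining the three 4-week recalls is open to the analyst and keeps the stated power (step 4). Table 2 also suggests a purpose for the past-summer mark at week 12, since weeks 0 and 64 carry the same mark; it may be there to match them. The documents do not say so, but neither do they point to it as the powered endpoint.

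The size of the loss is assumption-bound as well. No section gives the number of pre-device summer weeks. Section 11.1 places recruitment in spring with the intervention over the summer. The 16-week lottery shows only that starts may spread over about 4 weeks (16 − 12), not that each participant has that much summer before the device. At 1 week the loss is about 5 points.

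All of this stands, and it limits the point to an undefined derivation and an unnamed main test. It does not remove the point: the one explicit univariate rule still leads away from the powered quantity.

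**Conclusion.** The point holds as a gap between what is powered and what is specified. Section 15.2 powers one 12-week proportion. Section 15.3 gives a per-time-point test and no derivation rule, and Table 2 has no single item with the 12-week window. On the plan's own rates, one 4-week window has roughly 27% to 39% power if it captures a third to a half of those who burn. The past-summer item has about 65% to 46% under 1 to 6 assumed pre-device weeks at the control rate. A combined 12-week indicator has 70%.

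That 70% has two conditions. It needs little information to be lost through missed week 4 or 8 surveys, because the 314 counts week 12 completers. It also needs 20% to be a fair 12-week control rate, whereas sections 2.1 and 2.2 report it for the past year. The primary outcome is unaffected. The change should be made before analysis.

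**What to change.** In 3.2 and 15.3, define sunburn during the intervention as at least one sunburn reported on any of the week 4, 8 or 12 four-week items. Name one between-arm chi-squared or logistic test of that indicator as its main analysis. Apply the multiple imputation already planned in 15.3 to missed week 4 or 8 reports. Label the per-window and past-summer comparisons as supportive.

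Reconcile the survey clock as well. Section 5.2 starts week 0 at the start of the intervention, while 6.2 counts weeks from randomization. Devices are mailed after randomization, so on the 6.2 clock the week 4 recall could include days before the device arrived.

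The cost is wording; every item is already collected and no change in sample size is needed to support the stated 70% on its own inputs. The downside is reliance on imputation for participants who missed week 4 or 8. Those with a burn on another survey are already classified, so it matters only for those with none reported.

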4.3. Biosafety: N/A

4.4. Stem Cells: N/A

5. Procedures Involved

[figure not shown]
5.1. Study Design:

The RCT among 368 eligible melanoma survivors will be conducted in two Waves (two consecutive summers), with planned adjustments to improve recruitment, compliance and participant retention between study Waves, see Figure 3. Wave 1 may enroll up to 184 participants, though given logistical constraints due to working from home during the pandemic, fewer may be recruited, with the plan to obtain the full 368 by the end of Wave 2.

Figure 3. Phase 2 Study Design.

PROTOCOL TITLE: Wearable device intervention to improve sun behaviors in melanoma survivors

VERSION DATE: 07/19/2021

5.2. Study Procedures –Randomized Controlled Trial:

Randomization. Following written consent and completion of the baseline survey, participants will be randomized with a 1:1 ratio to the intervention or control arm. Randomization will be stratified by age (<50 years, 50+ years), gender, years since melanoma diagnosis (<2 years, 2-5 years, 6-9 years) and highest melanoma stage (I, II, III/IV). We will use block randomization with random blocks of size 2 and 4 to improve balance. The staff recruiting and enrolling participants will be blinded to their randomization. The study statistician will use R to generate random sequence numbers based on the stratified, block randomization scheme and upload the allocation list to REDCap. Following consent and screening, the study coordinator at the University of Minnesota will randomize participants.

Study Initiation. Following randomization, participants will then be mailed their device in early summer (with appropriate version of the mobile app based on randomization) and study assigned log-in information. This will include a study-created user name to be used with the device/mobile app to allow for direct retrieval of the device-collected data by the study coordinator. Participants will also be provided written training materials. Participants will be provided with a study phone number and email to contact the study coordinator with any remaining technical issues or questions.

PROTOCOL TITLE: Wearable device intervention to improve sun behaviors in melanoma survivors

VERSION DATE: 07/19/2021

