10.1. Local Number of Participants to be Consented as Eligible for Recruitment (Verbal): 460

Local Number of Participants to be Consented to Full Study (Written): 390

11. Local Recruitment Methods

11.1. Recruitment Process:

Trained and experienced staff of HealthPartners Institute Center for Evaluation and Survey Research (CESR) will oversee the recruitment process. The CESR has been engaged in research both within the HealthPartners patient/member population and broader community for more than 15 years and is directed by a seasoned PhD survey methodologist and health services researcher, who oversees staff of

PROTOCOL TITLE: Wearable device intervention to improve sun behaviors in melanoma survivors

VERSION DATE: 07/19/2021

bachelors and masters-level employees with experience and training in survey, interview, chart-audit, and electronic data capture for research purposes. The CESR employs REDCap (Research Electronic Data Capture)³³ as a primary data capture and management platform.

To recruit the required sample size and ensure meaningful measures of protection sun exposure, participants will be enrolled in two cohorts (Wave 1 and 2) over two consecutive summers. Recruitment will occur in the spring with the study intervention running over the summer both years to account for seasonality.

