Potential participants identified by HealthPartners in the screening process will be randomly assigned to a mailing round (2 rounds of approximately n=500 each within each Wave). Each round will be mailed 2 weeks apart to ensure phone contact is proximal to the mail date. We will send potential subjects a letter on HealthPartners letterhead introducing the general nature of the study and the elements of informed consent, and notifying the participant that a study interviewer will soon call. Subjects will be provided a study phone-number, which they may contact if they would like more information about the study. The letter will state that the information obtained is confidential and that participation is voluntary. Next, within two weeks of sending each letter, an interviewer trained specifically on this study protocol will phone the subject to ask if he or she is willing to participate in the study if they have not opted out. The interviewer will obtain verbal consent to participate in the study and for their contact information (name, address, phone number) to be shared with members of the University of Minnesota research staff. If such consent is provided, it will be documented and their names and contact information will be so forwarded. All subsequent contact with these individuals in conjunction with this study will be conducted by study staff at the University of Minnesota

Once the goal of consenting participants has been reached for a given Wave, a wait-list will be created which will be used to replace individuals who do not complete the formal study consent process and baseline survey. Given our expectation of losing approximately 15% of individuals after this initial agreement, HealthPartners will provide the University of Minnesota with contact information for additional individuals.

The University of Minnesota staff will then contact individuals provided by HealthPartners by mail or email in spring to confirm their interest in participating in the study and obtain written or electronic informed consent and HIPAA forms along with their preferred form of contact for study communication.

PROTOCOL TITLE: Wearable device intervention to improve sun behaviors in

melanoma survivors

VERSION DATE: 07/19/2021

11.2. Identification of Potential Participants:

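### The within-arm baseline-to-week-12 paired t-tests mix season and other time effects with any intervention effect, so they cannot show whether the control group received one

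*Combined protocol and SAP*

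**What the plan says.** Section 15.3 states the purpose of the analysis, "To address any potential intervention effects in the control group", and then the method: "we will compare the baseline and post-intervention sun protection behaviors scores using paired t-tests, stratifying by randomization group". The outcome is the habits index of section 3.1, the mean of six behaviors scored 1 to 4.

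The timing of the two scores has to be pieced together:

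- **Recruitment (section 11.1):** "Recruitment will occur in the spring with the study intervention running over the summer both years to account for seasonality". The university team "will then contact individuals provided by HealthPartners by mail or email in spring to confirm their interest" and to obtain consent.
- **Baseline survey (section 5.2, Randomization):** "Following written consent and completion of the baseline survey, participants will be randomized with a 1:1 ratio".
- **Device delivery (section 5.2, Study Initiation):** "Following randomization, participants will then be mailed their device in early summer".
- **Recall window (Table 2):** the habits items carry a single asterisk at weeks 0, 4, 8, 12 and 64, which the footnote defines as "Time frame: past 4 weeks".
- **End point (section 5.2, Data Collection):** week 12 is the end of the intervention. Week 64 is one year later and is placed at the end of the next summer, so week 12 is also at the end of a summer.

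Under section 4.1, controls receive the device with a collection-only app and basic sun information on the website. No arm goes without both.

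**The concern.** The stated purpose is causal: to find out whether the control condition itself changed behavior. A paired t-test within one arm tests only whether the mean changed between two dates. Here those dates fall in different parts of the year, and the index covers sunscreen, hats, sleeves, shade, sunglasses and time in the sun, all of which could plausibly vary with season without any device.

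The result could mislead in two ways. A rise in controls that is only seasonal could be read as an effect of the device or website, and then offered as the reason for a null primary comparison. A seasonal fall could hide a real effect in controls. The same limit applies to the paired test in the intervention arm.

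**Working it through.** **1. The plan's own figures.** Section 15.2 gives 95% power with 314 evaluable participants, effect size 0.40 and two-sided 0.05. With 314/2 = 157 per arm, the two-sample calculation gives 0.943 (normal approximation) or 0.942 (noncentral t), which agrees. The sunburn figure, 20% versus 10% with 157 per arm, gives 0.701 against the stated 70%. The expected number of completers is 368 × 0.85 = 312.8, against the stated 314. The power section is not at issue. It gives no figure for the paired tests.

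**2. What each score describes.**

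| Survey | Placement | Four-week window covers |
|---|---|---|
| Week 0 | After spring contact, before randomization and the early-summer mailing | Roughly spring to early summer (inferred) |
| Week 12 | End of intervention, one year before a survey set at the end of summer | Late summer |

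**3. What the mean change contains.** In the control arm:

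mean change = season + repeated questioning + regression to the mean + any device or website effect.

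The paired test sees only the sum. Separating the last term needs a group that goes through the same calendar and surveys without the control components, and the trial has none. Eligibility in section 8.1 does not select on the habits score, so regression to the mean may be small; season and repeated questioning do not depend on such selection.

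**4. Illustration of size.** Inputs: n = 157 controls with both scores, from section 15.2. Assumptions not in the documents: equal SDs at the two surveys, within-person correlation r, a seasonal shift s in SD units, and no device effect.

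- SD of the change = √(2(1 − r)) in SD units.
- Noncentrality = s × √157 / √(2(1 − r)), with 156 degrees of freedom and critical value 1.975.
- For r = 0.5 the SD of the change is 1.00. At s = 0.20 the noncentrality is 0.20 × 12.53 = 2.51, and the probability of p<0.05 is 0.70.

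| Assumed shift | r = 0.3 | r = 0.5 | r = 0.7 |
|---|---|---|---|
| 0.10 SD | 0.18 | 0.24 | 0.36 |
| 0.20 SD | 0.56 | 0.70 | 0.90 |
| 0.25 SD | 0.75 | 0.88 | 0.98 |
| 0.30 SD | 0.88 | 0.96 | 1.00 |

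At r = 0.5, the smallest observed change that reaches p<0.05 is 1.975 × 1.00 / 12.53 = 0.16 SD.

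**5. Both directions, by simulation (4,000 runs, r = 0.6, 157 per arm).**

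| Scenario | Control paired test, p<0.05 | Intervention paired test, p<0.05 | Between-arm test of change, p<0.05 |
|---|---|---|---|
| Seasonal rise 0.20 SD, no effect in either arm | 80% | 80% | 4.9% |
| Seasonal fall 0.20 SD, true effect +0.20 SD in both arms | 4.8% | 4.9% | 5.4% |

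The first row shows a significant control change with no effect present. The second shows a real effect hidden. Comparing the arms removes season, but it also removes any effect common to both arms, which is the effect this analysis was meant to find.

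**The case against.** **Seasonality is already handled.** Section 11.1 says the schedule accounts for it. That makes the two waves comparable with each other; it does not put one participant's two surveys in the same season.

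**Spring is an inference.** This stands in part. Section 5.2 also calls week 0 the start of the intervention, and section 11.4 mentions rolling recruitment, so some baseline windows may reach early summer. Table 2 describes the items as use while in the sun, which may weaken the link with season. The gap may be narrower than spring to late summer, but the windows still lie at opposite ends of the intervention.

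**The percentages follow from the assumed shift.** This stands. No document gives the size or direction of a seasonal change. A reader might take 70% or 88% as the test's actual false-positive rate. They are not: if the season moves the mean, the hypothesis of no change is false and the test is right to reject it. The error lies in attributing the change to the intervention.

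**Other analyses bear on the question.** This also stands in part. The mixed model in section 15.3 includes the control trajectory, and Table 2 collects knowledge at weeks 0, 12 and 64. It would be too strong to call the paired tests the only relevant evidence, although they are the only analysis the plan names for this purpose. Within-arm change in the mixed model carries the same mixture of time effects.

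**Efficacy does not rest on these tests.** Correct. A reader might infer that season biases the primary result. It does not: the week 12 comparison is between randomized arms that share the same season.

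**Conclusion.** The concern holds for this one secondary analysis. The within-arm paired tests cannot answer the question section 15.3 gives them: a significant control change does not show an intervention effect, and a null change does not exclude one. That follows from the survey timing, the recall window and the lack of an untreated arm, not from any assumed number. The figures of about 70% at 0.20 SD and 88% at 0.25 SD (157 controls, r = 0.5) show only that a modest shift would be enough to produce a significant result.

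A reader might infer that a season-matched pair already in Table 2 could replace the test. The documents do not support this for week 12 versus week 64. Both scores follow exposure to the device and website, and section 7.1 gives every participant a personal exposure summary. An effect that persisted in controls would leave no difference to detect.

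Nor do the documents attach any decision rule to the paired tests. Their use to explain a null primary result is a risk to close off, not something the plan states.

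**What to change.** In section 15.3:

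1. Report the week 0 to week 12 change within each arm with a confidence interval, as description only.
2. State that this change mixes season and other time effects with any intervention effect.
3. Remove the statement that it addresses intervention effects in the control group, and say that it will not be used to explain a null primary result.
4. Optionally, show sunburn with the past-summer frame at week 0 and week 12 in controls as season-matched supporting description. Note that it is a different outcome, covers different calendar years and has a longer recall at week 0.
5. Do not substitute week 12 versus week 64 as the test.

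This is a wording change with no new data and no effect on sample size or the primary analysis. The cost is that the trial gives up a formal test of effects in controls, which its design cannot support.
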